## **9.2 Comparable Methods**

N/A

## **10. SPECIMEN MANAGEMENT**

### **10.1 Laboratories**

The University of Washington Research Testing Service (UW RTS) will result the UW clinical labs.

The University of Washington Laboratory Medicine will result the STAT UW clinical labs.

The University of Wisconsin Hospital and Clinics Clinical Laboratories will result the clinical labs at UWI.

The University of Washington Immunological Monitoring Lab (UW IML) will perform immune analysis for each research specimen.

The UW IML uses the Biological Specimen Inventory II (BSI-II) system, which is an established software system for bio-specimen management that includes tracking of specimen shipments via a web interface. It provides freezer, acquisition, entry, report, and requisition modules in a validated secure software environment that includes a full audit trail and is CFR 21 Part 11-compliant. All specimens received and processed in this laboratory are tracked using this system. Rates include general maintenance, data back-up and hosting of the SQL database by Information Management Services.

### **10.2 Collection and Handling Procedures**

Approximately 15 mls of blood will be drawn for clinical labs at each study visit.

Approximately 200 mls of blood for immunologic monitoring will be collected at the first vaccination visit, as well as, 1 month (28+7 days) and 6 months (168 ± 14 days) after the last vaccine. Research blood will be transported at ambient temperature until processed by the UW IML within approximately 34 hours of the blood draw. Specimens and plasma are then stored at approximately -80°C until use. Serum will be processed at each site and stored in a -80°C freezer and will be shipped to IML in batches. When whole blood is to be shipped overnight to the IML, it cannot be drawn on a Friday or a day prior to a holiday. Blood cannot be drawn or shipped on Friday or day prior to a holiday if it is being shipped overnight.

ELISPOT and FACS will be done on research samples in batches by the UW IML. Serum samples will be stored and analyzed at the end of the study.

#### **Samples for future testing**

If any research blood is left over after the study's immunologic monitoring, it may be stored for future research related to the development of other immunotherapies. The choice to store any leftover samples is up to the patient and whatever their decision, it will not affect their participation in this study.

#### **10.3 Shipping Instructions**

Research specimens will be tracked from their point of origin to the UW-IML using BSI-II. All samples will be shipped in compliance with the International Air Transport Association (IATA) Dangerous Goods Regulations.

Research specimens (blood) by the clinical team will be collected at UW and UWI. UW-collected specimens will be transported by the clinical team or a courier to the UW-IML for processing. UWI-collected specimens will be shipped via FedEx to the following location:

All research specimens should be shipped to the following location (UWI: via FedEx; UW will courier samples):

UW Immune Monitoring Laboratory  
Attn: [name]  
University of Washington Tumor Vaccine Group  
[name]  
[name]  
[name]

To contact the UW IML Laboratory:

Email: [contact]  
[contact], Monday-Friday 8:00 AM - 4:30 PM PST  
Before/after hours [contact] (for emergencies only)

#### **10.4 Tissue Banking**

Tissue will not be banked for this study.

### **11. REPORTING ADVERSE EVENTS**

**DEFINITION:** AE means any untoward medical occurrence associated with the use of a drug in humans, whether or not considered drug related. An AE can therefore be any unfavorable and unintended sign, symptom, or disease temporally associated with participation in a study, whether or not related to that participation. This includes all deaths that occur while a patient is on a study.

Please note that all abnormal clinical laboratory values that are determined to be of clinical significance based on clinician's assessment are to be reported as AEs. Patients with a clinically significant clinical

laboratory AE ongoing at the last visit will be followed for up to 6 months or resolution to baseline, whichever is shorter.

Those labs determined to be of no clinical significance or of unknown clinical significance (per the clinician's assessment) should not be reported as AEs. Any lab value of unknown clinical significance should continue to be investigated/followed-up further for a final determination, if possible.

For blood glucose measurements: All fasting glucose measurements  $\geq 100$  mg/dL per Section 8.5.1.1 should be reported as an AE.

A list of expected AEs that we have seen in previous vaccines can be found in §6.2., Reported adverse events and potential risks, as well as, in the Pharmaceutical Information, or the Investigator's Brochure.

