We have experience immunizing with two of the three components of WOKVAC in our clinical plasmid; HER2 and IGFBP-2. We have completed a 66 patient study of pUMVC3-HER2 ICD. Immunizing advanced stage breast cancer patients against pUMVC3-HER2 ICD did not result in significant toxicity. A total of 990 adverse events (AEs) were recorded. Ninety-nine percent of collected AEs were grades 1 and 2, but only 52% of those recorded were possibly, probably or definitely related to vaccination. The most common AEs were reaction at the injection site, and flu-like syndrome. All reactions at the injection site were attributable to the vaccine; however, only 82% and 78% of the fatigue and flu-like syndrome, respectively, were attributable to the vaccine. pUMVC3-HER2 ICD also did not induce clinically significant autoimmunity. We evaluated for the development of serologic autoimmunity, only four patients exhibited decreased complement C3, 2 patients had a positive antinuclear antibody (ANA) defined by titers of  $\geq 1:160$  by immunofluorescence (IF) and no patient developed clinical evidence of autoimmune disease. Lymphocytes from study patients were evaluated for presence of vector pre- and 1 month post-vaccination. If persistent DNA was detected at 1 month, serial assessment for vector presence was continued at 3, 6, and 12 months after the last vaccine, or until DNA was no longer detected. There was no detection of DNA plasmid in lymphocytes from patients immunized. No significant vaccine induced cardiac toxicity was observed and all cardiac toxicities observed on the study were either Grade 1 or Grade 2. In addition, those patients receiving concurrent trastuzumab during vaccination (n=31) across all arms, the median LVEF pre- and post-vaccination was 61% and 60%, respectively.

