## 8. CRITERIA FOR EVALUATION AND ENDPOINT DEFINITION

### 8.1 Primary Endpoint

A primary endpoint of the study is safety. Safety of the three escalating dose of WOKVAC will be assessed by adverse events as per CTCAE v4.0.

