#### 8.5.1. Criteria for Premature Study Termination

Benchmarks for the safety of a dose level will be that there are no attributable (definitely, probably and possibly-related to study drug) grade 4 toxicity and <30% incidence of attributable Grade 3 toxicity (definitely, probably and possibly related to the study agent except as noted in the table below). If the observed rate of each of these toxicities is consistent with these benchmarks, escalation to the next higher dose level will be allowed.

Escalation will not be allowed if the observed toxicity rate exceeds the above. Other participants at the same dose level without toxicities will be allowed to continue at that dose level.

For grade 1 or 2 vaccine-related reactions, patients may be treated with acetaminophen or diphenhydramine as clinically indicated at the discretion of the study clinician and continue to receive vaccinations. For this prevention study  $\geq$  grade 3 attributable toxicity (other than those listed below; CTEP CTCAE v4.0) is considered dose-limiting for the patient. If grade 3 toxicity that is at least possibly related to the vaccine (except as described below) is observed, no further immunizations will be administered to that patient.

If  $\geq 3$  participants experience a grade 3 attributable toxicity, except as noted in the table below, or if any participant experiences a grade 4 attributable toxicity within any dose level, further accrual at that dose level will stop and accrual to the study will be terminated.

Category	Grade 3 Attributable Toxicity/AE	Allowable Duration
General disorders and administration	Flu-like symptoms	1 week
Musculoskeletal and connective tissue disorders	Arthralgia	1 week
	Myalgia	1 week
Investigations	Lymphocyte count decreased	2 weeks
	Platelet count decreased	1 week
	Hemoglobin decrease	1 week
	White blood cells decreased	2 weeks

We would consider a grade 3 or 4 autoimmune event a dose limiting toxicity and would consider steroid administration for grade 3 or 4 adverse immune related events that have been reported with other immune based therapies, i.e. ipilimumab. Examples of such immune related AEs include; rash, diarrhea/colitis, and hepatitis. The following dose schedule may be used:

Day 1-2: Intravenous Solu-Medrol at 1 mg/kg  
Day 3-4: Prednisone at 30 mg BID PO q day  
Day 4-5: Prednisone at 15 mg BID PO q day  
Day 5-6: Prednisone at 10 mg BID PO q day  
Day 6-7: Prednisone at 10 mg PO q day  
Day 8-9: Prednisone at 5 mg PO q day

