### **13.4 Primary Objective, Endpoint(s), Analysis Plan**

A primary endpoint of the study is safety through the 6 month follow-up visit. Safety of the three escalating dose of WOKVAC will be assessed by adverse events as per CTCAE v4.0.

The type and grade of toxicities noted during the immunization regimen will be summarized. The duration of toxicities will also be summarized using descriptive statistics such as mean and standard deviation. All adverse events noted by the investigator will be tabulated according to the affected body system. The frequency and severity of adverse events will be summarized with a proportion and a 95% confidence interval. Despite lack of randomization, the incidence and severity of toxicity will be compared between successive dose groups using nonparametric test with the understanding that due to small sample size per dose group such test will have limited sensitivity to detect any small to moderate differences. These tests will be performed without adjustment for multiplicity of testing.

Demographic and baseline characteristics obtained at enrollment will be summarized in tabular or graphical formats with descriptive statistics.

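### Laboratory abnormalities called of no or unknown significance stay out of the AE data at any grade, no other laboratory summary is planned, and Section 8.5.1 does not say whether they count.

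*Combined protocol and SAP*

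**What the plan says.** - **Primary endpoint (8.1, repeated in 13.4).** "Safety of the three escalating dose of WOKVAC will be assessed by adverse events as per CTCAE v4.0". For the analysis, 13.4 states: "All adverse events noted by the investigator will be tabulated according to the affected body system".
- **Which laboratory values become AEs (Section 11, opening).** Abnormal values "determined to be of clinical significance based on clinician's assessment are to be reported as AEs". The complementary rule keeps out "Those labs determined to be of no clinical significance or of unknown clinical significance". Neither sentence mentions grade. A value of unknown significance "should continue to be investigated/followed-up further for a final determination, if possible", with no deadline and no interim status.
- **One objective exception.** "All fasting glucose measurements" of 100 mg/dL or more under 8.5.1.1 are AEs regardless of judgement.
- **Grade 3-4 follow-up (11.1.5).** Follow-up of laboratory abnormalities again depends on the investigator's opinion of clinical significance.
- **Stopping and escalation (8.5.1).** A dose level stops at three or more participants with attributable grade 3 toxicity, or at one with attributable grade 4. A table excepts certain grade 3 events for a limited time, including four blood counts: lymphocytes and white cells for 2 weeks, platelets and hemoglobin for 1 week. The row "Lymphocyte count decreased", like the others, carries a grade and a duration and no significance test.
- **Blinding (6.9).** There is none.
- **Data collected (2.2, Section 3, 7.1).** CBC, CMP, ANA, anti-dsDNA, C3, TSH, GAD65, HbA1c and LVEF are scheduled. Sections 2.2 and 3 describe the clinical and autoimmune laboratory tests and LVEF as safety evaluations.

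**The concern.** The endpoint is named as CTCAE toxicity, but the laboratory part reaches the analysis only after a clinician who knows the dose has decided that a value matters. That filter can remove laboratory events and cannot add any, so any bias relative to complete grading is downward. Nothing in Section 13 offsets it, because no table is planned from the laboratory values themselves.

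Two things are at stake in a first-in-human trial. The first is the reported safety profile by dose. Asymptomatic serologic change is the kind of result most easily called not significant, and it is also what the sponsor found informative before: Section 2.2 reports, for the HER2 plasmid trial, that "only four patients exhibited decreased complement C3". The second is the count behind escalation and termination. With a threshold of three patients, one patient can decide the outcome, and three sections of the protocol do not agree on whether that patient is counted.

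**Working it through.** **Plan's own figures.** The plan gives no operating characteristics for the 8.5.1 rule and no expected laboratory event rate, so there is nothing to reproduce on this point. Its only power figure is 0.80 in 13.5 for the dose-response regression. That reproduces (noncentral F, 1 and 28 df, noncentrality 0.281 × 30 = 8.43, power 0.800) but does not bear on safety.

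**Following one value through the text.** Take an attributable grade 4 platelet count, or a grade 3 count lasting beyond its allowable week, that the clinician calls of unknown significance.

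1. Section 11: it is not an AE for now. It is pursued if possible.
2. Section 13.4: it is not an AE, so it is not tabulated.
3. Section 11.1.5: follow-up to resolution applies only if the investigator considers it clinically significant. Scheduled CBCs around the vaccinations are 28 (+7) days apart, so a duration of 1 or 2 weeks can be established only by repeat testing.
4. Section 8.5.1: by grade, attribution and duration it qualifies for the count. If toxicity there means a recorded AE, it does not.
5. Section 13.10: the escalation review refers back to 8.5.1 and 13.4 and does not resolve the question.

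No section says that a grade 3 or 4 laboratory value is recorded or counted regardless of the significance call.

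**Size, as sensitivity only.** Let p be the true proportion of patients with a qualifying grade 3 event, and s the share of those patients whose only qualifying event is a filtered laboratory value. The documents give neither; both are assumptions. With n patients and q = p(1 − s),

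P(3 or more) = 1 − Σ C(n,k) q^k (1 − q)^(n−k), k = 0, 1, 2.

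For n = 10 (13.9):

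| p | s = 0 | s = 0.25 | s = 0.50 |
|---|---|---|---|
| 0.10 | 0.070 | 0.034 | 0.012 |
| 0.20 | 0.322 | 0.180 | 0.070 |
| 0.30 | 0.617 | 0.398 | 0.180 |

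For n = 12 (the maximum in 13.3) and p = 0.30 the row is 0.747, 0.528, 0.264. For the grade 4 rule (one or more of 10) with p = 0.05 it is 0.401, 0.318, 0.224.

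**Which rows are plausible.** Section 2.2 gives ceilings that cover all event types and causes.

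- HER2 plasmid trial: 99% of 990 AEs were grade 1-2, leaving about 0.01 × 990 ≈ 10 events in 66 patients, so at most about 10/66 = 15% of patients.
- IGFBP-2 trial: 96% of 208 AEs were grade 1-2, leaving about 0.04 × 208 ≈ 8 events in 25 patients, so at most about 8/25 = 32%, and only if each event fell in a different patient.

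Attributable laboratory events are some unknown subset of these. At p = 0.05 the unfiltered chance of reaching three of 10 is already only about 0.012.

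**The case against.** Several points on the other side stand, and they rule out stronger readings.

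- A reader might infer that 8.5.1 counts every grade 3 blood count. It does not. The four counts are exceptions within 1 or 2 weeks, so at grade 3 only prolonged ones are at issue. Grade 4 has no such exception.
- A reader might infer that values of unknown significance are lost for good. The text makes that a pending state, and a value later judged significant becomes an AE. What is missing is a deadline, so the determination may come after an escalation decision.
- A reader might infer that laboratory data are used nowhere. Section 13.1 brings other laboratory findings into the phase 2 dose review. That review is unspecified and takes place after Arm 3, so it does not replace a tabulation during escalation.
- A reader might infer that silent autoimmune changes will go unreported. Section 11 governs AE labelling and does not bar reporting of collected data. The supportable statement is that no such report is planned.
- LVEF is imaging and is not covered by the laboratory filter. It also has a lower-limit-of-normal check before vaccine 2 (7.4.2). For LVEF the gap is only the missing summary.
- The glucose exception is not an admission that the filter is unsuitable, since hyperglycemia is a named risk (2.2, 6.2). It shows only that an objective rule is workable for one test.

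Clinician judgement of laboratory values, and open-label attribution (11.1.4), are usual in phase I, and attribution would remain under any fix. That does not answer the point, which is that no objective tabulation stands beside the judged data and that three sections leave the count ambiguous.

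**Conclusion.** The concern holds for the laboratory part of the primary safety result. Symptomatic AEs are recorded whether or not related (11.1.1) and are unaffected. Qualifying fasting glucose values are exempt from the filter. The direction of any bias is downward. Its size cannot be computed, because the documents give neither the true rate nor the share filtered out. What is certain is the leverage: one patient is 1/10 = 10 percentage points in an arm of 10, and two against three patients separates continuing from terminating.

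A reader might take the fall from 0.617 to 0.180 as an estimate of lost stopping probability. It is not. It assumes a 30% qualifying rate and a 50% filtered share, neither of which has a source. That rate is about twice the 15% ceiling from the HER2 plasmid trial and close to the 32% ceiling from the smaller IGFBP-2 trial, and both ceilings cover events of every type.

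Separately, Sections 8.5.1, 11 and 11.1.5 conflict on whether a prolonged grade 3, or any grade 4, attributable laboratory value called not or unknown significant is counted. This should be fixed, but it does not invalidate the design.

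**What to change.** 1. **Section 13.4, reporting.** Derive CTCAE v4.0 grades by program from all scheduled CBC and CMP values for which CTCAE gives numeric grades. Beside the AE table, report by arm the worst post-baseline grade and the shift from baseline to worst grade. Add patient counts by arm for ANA at 1:160 or higher (the definition used in 2.2), anti-dsDNA, low C3, abnormal TSH, GAD65, HbA1c, and LVEF below the institutional lower limit. Have these tables ready for each dose-level review under 13.10. They show grade at scheduled visits and cannot by themselves establish the durations in 8.5.1.
2. **Sections 8.5.1, 11 and 11.1.5, consistency.** Reconcile them so that the protocol states how an attributable grade 3 or 4 laboratory value called of no or unknown significance enters the 8.5.1 count, and what its status is while the determination is pending. Which rule to adopt is for the sponsor and its medical monitors; this review does not choose one.

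The cost is SAP and protocol wording and a few tables from data already scheduled in 7.1. The downside is that more low-grade laboratory findings will be listed.

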## **11.1 Adverse Events**

### **11.1.1 Reportable AEs**

AEs that occur after the informed consent is signed and baseline assessments are completed (including run-in) must be recorded on the AE Case Report Form (paper and/or electronic) whether or not related to study agent. AEs including Serious Adverse Events (SAEs) will be collected through the 6-month follow-up visit.

### **11.1.2 AE Data Elements:**

The following data elements are required for adverse event reporting:

- CTCAE (MedDRA) System Organ Class (SOC)
- NCI Common Terminology Criteria for Adverse Events v4.0 (CTCAE) AE term (MedDRA lowest level term)
- Event onset date and event ended date
- Severity grade
- Attribution to study agent (relatedness)
- Whether or not the event was reported as a serious adverse event (SAE)
- Whether or not the patient dropped due to the event
- AE verbatim term
- Action
- Outcome
- Treatment assignment code (TAC) at time of AE onset

### **11.1.3 Severity of AEs**

11.1.3.1 Identify the AE using the NCI Common Terminology Criteria for Adverse Events CTCAE v4.0. The CTCAE v4.0. provides descriptive terminology (MedDRA lowest level term) and a grading scale for each adverse event listed. A copy of the CTCAE 4.0 can be found at [http://ctep.cancer.gov/protocolDevelopment/electronic\\_applications/ctc.htm](http://ctep.cancer.gov/protocolDevelopment/electronic_applications/ctc.htm).

AEs will be assessed according to the grade associated with the CTCAE v4.0 AE term. AEs that do not have a corresponding CTCAE v4.0 term may be assessed according to the general guidelines for grading used in the CTCAE v4.0 as stated below.

## CTCAE v.4.0 general severity guidelines:

Grade	Severity	Description
1	Mild	Mild; asymptomatic or mild symptoms; clinical or diagnostic observations only; intervention not indicated.
2	Moderate	Moderate; minimal, local or noninvasive intervention indicated; limiting age-appropriate instrumental activities of daily living (ADL)*.
3	Severe	Severe or medically significant but not immediately life-threatening; hospitalization or prolongation of hospitalization indicated; disabling; limiting self-care ADL**.
4	Life-threatening	Life-threatening consequences; urgent intervention indicated.
5	Fatal	Death related to AE.

\*Instrumental activities of daily living (ADL) refers to preparing meals, shopping for groceries or clothes, using the telephone, managing money, *etc.*

\*\*Self-care ADL refers to bathing, dressing and undressing, feeding self, using the toilet, taking medications, and not bedridden.

### 11.1.4 Assessment/Attribution of relationship of AE to treatment.

The possibility that the adverse event is related to study agent will be classified as one of the following attributions: unrelated, unlikely, possible, probable, definite.

### 11.1.5 Follow-up of AE's

Clinically significant laboratory Adverse Events will be reported to the participant to have them follow up with their primary care physician. That conversation will be documented in the research chart. Grade 3 or 4 AEs including lab abnormalities, which in the opinion of the investigator, are clinically significant, will be followed until resolution to baseline or stable.

## 11.2 Serious Adverse Events

11.2.1. DEFINITION: Regulations at 21 CFR Section 312.32 (revised April 1, 2014) defines serious adverse events (SAEs) as any untoward medical occurrence that at any dose has one or more of the following outcomes:

- a. Death.
- b. A life threatening AE
- c. Inpatient hospitalization or prolongation of existing hospitalization.
- d. A persistent or significant incapacity or substantial disruption of the ability to conduct normal life functions.
- e. A congenital abnormality/birth defect.
- f. Important medical events that may not be immediately life-threatening or result in death or hospitalization should also be considered serious when, based upon appropriate medical judgment, they may jeopardize the patient and may require intervention to prevent one of the other outcomes.

